2.1.3 Additional Data Collection

Clinical Outcomes:

Clinical outcomes will be evaluated with the total HHS, including pain, motion and function, preoperatively and at the 6-week, 1, 2 and 5-year visits. Additional HHS data will be obtained at the 7-year and 10-year time points at investigational sites that choose to bring their subjects in for these optional visits.

Patient Outcomes:

Pain, function and health related QOL will be compared between the Secur-Fit Advanced Hip Stem and reports in the literature for other primary femoral stems on the market. The SF-12 is a 12 item patient self-assessment evaluating health and general well-being. The LEAS is a tool that has been developed and validated to evaluate the level of patient activity. The EQ-5D is a standardized instrument for use as a measure of health outcome. These tools will be used to assess patient health-related QOL and will be collected preoperatively and at the 6-week, 1, 2, 3, 4, and 5-year time points.

A Follow-up Questionnaire will be administered annually in postoperative years 3, 4 and 6-10 to assess patient satisfaction and pain, and to capture AEs. This questionnaire, which will also be completed during each interval through 5 years postoperative at which the subject is not seen by the investigator, will provide the information necessary to create an accurate Kaplan-Meier Survival Curve. Patient outcomes data will also be obtained at the 7-year and 10-year time points at investigational sites that choose to bring their subjects back in for these optional visits, in addition to the required Follow-up Questionnaire described.

Radiographic Outcomes:

To assess radiographic stability as compared with other primary femoral stems, radiographs will be taken and collected in the low AP pelvis and Lauenstein lateral views for the preoperative, 6-week, 1, 2 and 5-year intervals. Additional radiographs will be obtained at the 7-year and 10-year time points at investigational sites that choose to bring their subjects back in for these optional visits.

The low AP pelvis view allows for measurement of the position of the hip center, femoral offset and neck angle, and any leg length discrepancy. The Lauenstein lateral view allows for evaluation of the entire hip joint as well as the femoral head, neck and proximal shaft. Suggested radiographic technique for the views required is included in Appendix C.

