7.4 Annual Follow-up Visits

Clinical data will be collected via office visit by the investigator at the following annual

postoperative intervals: 1-year, 2-year and 5-year. Tools for postoperative evaluation at each of

these intervals will be the HHS, AP pelvis and Lauenstein lateral radiographs. In the event that

an in-person visit cannot be conducted and radiographs cannot be obtained, a Follow-up

Questionnaire will be completed via mail, online completion (if available), or telephone interview

with the subject by investigative site personnel.

Patient outcomes data will also be collected with the Follow-up Questionnaire, SF-12, LEAS, and

EQ-5D patient questionnaires at each office visit and at the 3-year and 4-year intervals via mail

or online completion, if available.

All clinical data, radiographs, and patient outcomes data must be collected within ± 2 months of

the 1-year and 2-year anniversary dates. For remaining annual time points, the window expands

to ± 3 months of the 3-year anniversary date and ± 4 months of the 4-year through

10-year anniversary dates.

The initial phase of the study will continue for 5 years after surgery and include collection of the previously described radiographs, HHS, SF-12, LEAS and EQ-5D patient questionnaires. In the second phase of the study, all subjects will complete a brief Follow-up Questionnaire annually at the 6-year, 7-year, 8-year, 9-year and 10-year follow-up intervals. This form may be completed by the SC during a subject telephone interview, or by the subject either at home or during a clinic visit. The questionnaire will be used to obtain the following information, at a minimum:

- Subject satisfaction with the hip replacement
- Presence of any pain in the study hip
- Any surgeries performed on the study hip

The questionnaire will also provide information on any revisions and enable calculation of the Kaplan-Meier Survival Curve.

Additionally, at investigational sites that choose to continue collecting clinical and radiographic data during the second phase of the study, subjects will be evaluated again at 7 and 10 years after surgery.

8 Adverse Events

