9.4.2 Sample Size Justification

With a reference value of 99% of success rate at 5 years, under the regular assumptions of 5% significance level (or 95% one-sided confidence interval), 80% power, 2.5% non-inferiority margin, the sample size is 277. After factoring a 15% lost to follow-up rate, the final sample size is 326. A significant decrease in screening/enrollment occurred after 2018, resulting in a final sample size of 314 cases.

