10.3 Early Withdrawal of Subjects

When and How to Withdraw Subjects

In the event that the subject is discontinued by the investigative center prior to the final study evaluation, the subject will be notified by the center that he/she is no longer in the study and a Study Termination eCRF will be completed.

The following is a list of reasons for which subjects may be withdrawn and the date of termination that should be used on the Study Termination eCRF in each situation. This list is not all inclusive:

Termination Reason	Date of Termination
Death	Date of death
Investigative center termination	Date of study close-out visit
Lost to follow-up	Date Stryker termination approval given
Voluntary withdrawal	Date subject notified center of withdrawal
Revision/removal of study device	Date of revision/removal procedure
Study device not implanted	Date of surgery
Surgery not performed	Date Stryker termination approval given

At the time of study surgery it is required that the following components are implanted for each treatment group:

Secur-Fit Advanced Hip Stem with any compatible Stryker acetabular components:

- o Secur-Fit Advanced Hip Stem
- Compatible Stryker femoral head
- o Compatible Stryker acetabular insert
- Compatible Stryker acetabular liner (if used)
- o Compatible Stryker acetabular shell

Revision or removal of the Secur-Fit Advanced Hip Stem for device-related femoral fracture or aseptic loosening constitutes a failure. Revision or removal of the Secur-Fit Advanced Hip Stem for any reason requires study termination for the subject.

If revision of the femoral head or any acetabular component is required during the study, the event does not constitute a failure or study termination.

If the subject fails to return for his/her follow-up appointments, every effort should be made to contact the subject to assess his/her health status. If, after attempting to contact the subject through three documented phone calls and a certified letter, the subject still does not respond, he/she will be considered lost to follow-up. A Study Termination eCRF will be completed only after notifying Stryker of the subject's status and being given approval to terminate.

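### The lost-to-follow-up rule lets one unanswered set of contact attempts end follow-up before year 5, with no later contact or 5-year stem-status check required

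*Combined protocol and SAP*

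**What the plan says.** Section 10.3 first sets a standard of effort for a subject who misses follow-up appointments: "every effort should be made to contact the subject to assess his/her health status". It then gives the threshold: after "three documented phone calls and a certified letter, the subject still does not respond, he/she will be considered lost to follow-up". Lost to follow-up appears in the same section's list of termination reasons, dated by "Date Stryker termination approval given". The termination form may be completed only after the sponsor has been told and has agreed. For a subject discontinued by the center, "the subject will be notified by the center that he/she is no longer in the study and a Study Termination eCRF will be completed".

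Before termination, a missed visit is covered. Sections 7.3 and 7.4 allow a Follow-up Questionnaire by mail, online or telephone when the 6-week, 1-, 2- or 5-year visit cannot be held. Section 2.1.3 adds: "This questionnaire, which will also be completed during each interval through 5 years postoperative at which the subject is not seen by the investigator", and says that it "will provide the information necessary to create an accurate Kaplan-Meier Survival Curve". In years 6 to 10 the questionnaire goes to all subjects, may be done by telephone, and asks about surgery on the study hip (7.4).

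On the analysis side, section 9.3 rules out imputation, and section 9.4.4 restricts the primary analysis to non-censored subjects available for efficacy evaluation. Section 9.4.2 states: "After factoring a 15% lost to follow-up rate, the final sample size is 326". It then gives 314 as the final number.

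**The concern.** The rule in 10.3 is written for a visit-based outcome, where a missed visit means a lost measurement. The primary endpoint is different. Whether a stem was revised, when and for what cause is a dated fact that can be established months or years afterwards. A subject who is silent at year 2 but answers at year 6 can supply the 5-year result.

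Section 10.3 gives no period over which the attempts must run, no minimum number of missed visits, no further attempt at the next annual interval, and no check of stem status after termination. The same threshold applies at 6 weeks and at year 9. A site that follows the text exactly may therefore stop trying well before year 5.

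Two things are at stake. Evaluable subjects are lost when some of that loss could be avoided. The loss may also be informative: someone who had the stem revised at another hospital has a reason not to come back. In a study where a handful of events decides the conclusion, the second matters more.

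**Working it through.** **1. The sections side by side.**

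| Question | What the plan provides |
|---|---|
| What makes a subject lost? | Three documented calls and a certified letter, no reply (10.3) |
| Spacing of attempts or number of missed visits? | Not stated |
| What follows? | Termination, after sponsor notification and approval (10.3) |
| Contact at later annual intervals after termination? | Not required, not forbidden |
| Can 5-year status be learned later? | Yes: the year 6-10 questionnaire asks about surgery on the study hip (7.4) |
| How is unknown status handled? | No imputation (9.3); evaluable subjects only (9.4.4) |

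Taken together, a subject terminated before year 5 with unknown stem status drops out of the primary analysis, and no section calls for the contact that could bring that subject back. Loss after 5-year status is known does not affect the primary endpoint.

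**2. The plan's sample size, reproduced.** Inputs from 9.1.3 and 9.4.2: reference 99%, margin 2.5 points (null 96.5%), one-sided 5%, power 80%.

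- n = ((1.645 × √(0.965 × 0.035) + 0.8416 × √(0.99 × 0.01)) / 0.025)² = 238.4
- With continuity correction: n/4 × (1 + √(1 + 2/(n × 0.025)))² = 277.0, the plan's 277
- 277 / 0.85 = 325.9, the plan's 326

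**3. Scale of the planned loss.** 314 × 0.15 = 47.1, about 47 subjects. 314 × 0.85 = 266.9, about 267 evaluable. The 15% is a planning allowance, not a count of subjects who would be terminated under this rule.

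**4. How few events decide the result.** The plan does not name its interval method. Assuming an exact (Clopper-Pearson) 90% two-sided interval, the lower bound must exceed 96.5%:

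- 4 failures in 267: 96.60%, passes
- 5 failures in 267: 96.10%, fails

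The smallest number evaluable at which 5 failures pass is 298. So if 4 failures were observed in 267 and one lost subject had an unlearned qualifying revision, counting it would give 5 in 268 and reverse the conclusion.

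**5. Why no power gain follows.** Recovering 10 subjects (277 − 267) is 10/47 = 21% of the planned loss. At a true rate of 99%:

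| Evaluable | Continuity-corrected formula | Exact interval | Failures tolerated (exact) |
|---|---|---|---|
| 267 | 77.6% | 86.8% | 4 |
| 277 | 80.0% | 85.3% | 4 |

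The apparent gain exists only under the first formula. Under the exact interval, power falls slightly, because the tolerated number of failures stays at 4. It rises only at 298 (5 tolerated, 91.9%), which needs 298 − 267 = 31 recovered, or 31/47 = 66% of the planned loss. The documents give no basis for any recovery rate.

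**The case against.** The strongest reply is that 10.3 is already a reasonable rule. It asks for every effort, sets a documented minimum, and separates being considered lost from being terminated. The sponsor can withhold approval and so keep a subject active. A missed visit alone does not trigger the rule, because the questionnaire fallback comes first. Only someone silent to visit, questionnaire, calls and letter reaches it. Differential revision risk among the lost is a hazard of any long study, and the documents put no figure on it.

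Much of this stands, and it rules out some stronger readings. A reader might infer that a non-responder is shut out permanently and that later contact is never tried. The text does not say so: it is silent on re-contact and re-entry and forbids neither. Nor does it say that one missed visit is enough, since it speaks of appointments in the plural and gives no count. A reader might also object that years 3 and 4 lack a telephone route, because section 7.4 collects patient outcomes data "at each office visit and at the 3-year and 4-year intervals via mail" or online. But the calls required by 10.3 would reach a year-3 or year-4 non-responder by telephone, so that point adds little.

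What the reply does not answer is the gap after termination. Sponsor approval has no stated criteria and adds no later contact. The fallback questionnaire applies to subjects still in the study. Nothing in the plan uses the year 6-10 contacts to recover the 5-year status of someone who was silent earlier.

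**Conclusion.** The concern holds in this form: one unanswered set of three calls and a certified letter can, with sponsor approval, end follow-up before the primary endpoint, and no section requires later annual contact or a 5-year stem-status check. Because the analysis neither imputes nor includes subjects with unknown status, the loss falls directly on the primary result, and it is partly avoidable.

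Its size cannot be given. The documents do not say how many lost subjects would answer a later contact or whether their revision risk differs, so the bias is a risk and not a demonstrated effect. A reader might infer that recovering ten subjects restores the planned power. That should not be claimed, since it depends on the choice of formula and reverses under an exact interval. The single-event sensitivity rests on an assumed exact interval and on the plan's 15% loss.

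The change should be made: it is cheap, concerns follow-up contact only, and protects an endpoint that stays observable. None of the plan's stated figures needs correcting on this account.

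**What to change.** In 10.3, when the calls and letter go unanswered, record the visit as missed and keep the subject active unless consent has been withdrawn. Repeat the Follow-up Questionnaire by mail, online or telephone at each later annual interval through year 10. Make lost to follow-up a final status only at study end.

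On renewed contact, record any stem revision since the last known status, with its date and cause. In section 9, state that stem status documented at or after 5 years, including on a year 6-10 form, counts as the observed 5-year result. This is late observation, not imputation, so it is consistent with 9.3.

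Cost: protocol wording, and about one extra mailing or call per silent subject per year. The downside is slightly more site effort and some subjects left open until study end.

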11.1 Database

Data will be collected at each center and entered into Stryker's Electronic Data Capture (EDC) system. The system can be accessed remotely by each investigative center and the data entered will be managed by Stryker. Subject data will be processed and monitored according to the protocol schedule by Stryker or Stryker representatives. Draft specifications to support eCRFs are provided in Appendix H.

11.2 Confidentiality

This study will comply with the 2002 HIPAA privacy rule. As such, Stryker will only collect that information which is necessary to support the objectives of the clinical study. Stryker will take precautions to ensure that data received is as de-identified as possible. In the case that some identified information is received, Stryker will ensure that any identifying information is not reported. Study subjects will authorize Stryker to use their health information in support of the clinical study during the informed consent process. Should a subject choose to withdraw authorization, Stryker may use data collected prior to the withdrawal of authorization in order to maintain data integrity.

11.3 Source Documents

Source data include all information, original records of clinical findings, observations or other activities in a clinical study necessary for the reconstruction and evaluation of the study. Source data are contained in source documents. Examples of these original documents and data records include: hospital records, clinical and office charts, study worksheets, laboratory notes, memoranda, subject questionnaires, pharmacy dispensing records, recorded data from automated instruments, radiographs, subject files, and records kept at the pharmacy, at the laboratories and at medico-technical departments involved in the clinical study.

All data points collected during preoperative and follow-up visits must be documented in the subject's chart. This includes range of motion values, pain and function as well as AEs and additional comments. The informed consent process should also be documented in the patient chart. Monitors, defined further in Section 13, will be comparing the eCRFs against source documents for adequacy. The monitors will seek to draw a reference between each data point on the eCRF and the subject's chart. Thus, one cannot derive pain, ROM or function based on a

chart note that reads "Patient doing well." Every effort should be made to ensure complete source documentation.

Centers are required to create a source documentation plan including any applicable source documentation worksheets prior to enrollment.

11.4 Electronic Case Report Forms

The study eCRFs are the primary data collection instrument for the study. All data requested on the eCRF must be documented. All missing data must be explained. It is recommended that eCRFs be completed and electronically signed by the investigator within 2 weeks of the evaluation date.

11.5 Data Clarification Requests

If errors or omissions are noted by Stryker upon review of the data entered into the eCRFS, a data clarification request (DCR) will be sent to the center within the EDC system. Queries should be answered in a clear and comprehensible manner. If the clarification requires a change to study data, the EDC system will update the eCRF automatically with the data captured in the DCR response. The investigative center will be required to reapply their electronic signature to the modified eCRF. Modified eCRFs need not be printed and included in conjunction to answered DCRs.

11.6 Protocol Deviations

Any deviation from this protocol will be recorded in Stryker's Clinical Trial Management System and must be reported to the EC/IRB by the investigational site according to their reporting procedures. Protocol Deviations for this study may include the following; this list may not be all-inclusive:

- Informed consent deviations, including but not limited to:
 - Study procedures performed prior to informed consent
 - Incorrect informed consent version used
- Patient enrolled does not meet the inclusion/exclusion criteria
- Protocol specified study component(s) not implanted
- Visit deviations, including:
 - Unavailable primary endpoint

If the center anticipates a possible protocol deviation, the investigator or SC should contact Stryker for guidance.

11.7 Records Retention

It is the investigator's responsibility to retain study essential documents for 2 years after the date of the final report, or in the case of non-compliance, 2 years after the date of investigative center termination. These documents should be retained for a longer period if required by an agreement with Stryker.

12 Risk/Benefit Assessment

12.1 Risk Category

There are no additional risks associated with participating in this study over and above that of the primary THA procedure.

12.2 Potential Risk

The study involves the routine assessment of a primary THA procedure. The Secur-Fit Advanced Hip Stem has been cleared for use by the FDA and will be used according to its labeling, included in Appendix I. Assessment involves questionnaires, patient and physician assessments as well as routine radiographs. The information collected will be kept confidential and will comply with the HIPAA privacy rule.

While the expected life of THA components is difficult to estimate, it is finite. These components are made of foreign materials, which are placed within the body for the potential restoration of mobility or reduction of pain. However, due to the many biological, mechanical and physiochemical factors which affect these devices but cannot be evaluated in vivo, the components cannot be expected to indefinitely withstand the activity level and loads of normal healthy bone.

Adverse effects associated with primary THA include the following:

Serious complications may be associated with any total joint replacement surgery. These complications include, but are not limited to: infection; genitourinary disorders; gastrointestinal

disorders; vascular disorders, including thrombus; bronchopulmonary disorders, including emboli;

myocardial infarction or death.

With all implanted devices, asymptomatic, localized progressive bone resorption (osteolysis) may

occur around the prosthetic components as a consequence of foreign-body reaction to the

particulate matter of metal, UHMWPE and/or ceramic. Particulate is generated by interaction

between components as well as adhesion, abrasion and fatigue. Secondarily, particulates can

be generated by third body wear. Osteolysis can lead to future complications, including loosening,

necessitating the removal and replacement of prosthetic components.

Early and late loosening of total hip components can occur. Early biomechanical loosening may

result from inadequate initial fixation, latent infection, premature loading of the prosthesis or

trauma. Late loosening may result from trauma, infection, biological complications including

osteolysis or mechanical problems, with the subsequent possibility of bone erosion and/or pain.

Dislocation of the hip prosthesis can occur due to inappropriate patient activity, trauma or other

biomechanical considerations.

Peripheral neuropathies, circulatory compromise and heterotopic bone formation may occur.

Intraoperative fissure, fracture, or perforation of the femur, acetabulum or trochanter can occur

due to impaction of the component into the prepared femoral canal or acetabulum. Postoperative

femoral or acetabular fracture can occur due to trauma, the presence of defects or poor bone

stock.

Metal sensitivity reactions have been reported following joint replacement.

AEs may necessitate reoperation, revision, arthrodesis of the involved joint, girdlestone or

amputation of the limb.

